### 7.2.3.1. Subgroup Analysis for Metabolic Laboratory Evaluations

The analysis of baseline, postbaseline, and change from baseline in fasting metabolic assessments will be summarized by treatment group and visit using descriptive statistics within each baseline F/TDF for PrEP medications subgroup specified in Section 3.4.2. Baseline and change from baseline will be compared between the 2 treatment groups using a 2-sided Wilcoxon rank sum test.

### 7.2.4. Liver-Related Laboratory Evaluations

Liver-related abnormalities after initial study drug dosing will be examined and summarized using the number and percentage of subjects who were reported to have the following laboratory test values for postbaseline measurements:

- Aspartate aminotransferase (AST): (a) > 3 × ULN, (b) > 5 × ULN, (c) > 10 × ULN,
   (d) > 20 × ULN
- Alanine aminotransferase (ALT): (a) > 3 × ULN, (b) > 5 × ULN, (c) > 10 × ULN,
   (d) > 20 × ULN
- AST or ALT: (a)  $> 3 \times ULN$ , (b)  $> 5 \times ULN$ , (c)  $> 10 \times ULN$ , (d)  $> 20 \times ULN$
- Total bilirubin: (a)  $> 1 \times ULN$ , (b)  $> 2 \times ULN$
- Alkaline phosphatase (ALP)  $> 1.5 \times ULN$
- AST or ALT >  $3 \times ULN$  and total bilirubin: (a) >  $1.5 \times ULN$ , (b) >  $2 \times ULN$
- AST or ALT > 3 × ULN and total bilirubin > 2 × ULN and ALP < 2 × ULN

The summary will include data from all postbaseline visits up to 30 days after permanent discontinuation of study drug or all available data for subjects who were still on study drug (regardless of study drug interruptions). For individual laboratory tests, subjects will be counted once based on the most severe postbaseline value. For both the composite endpoint of AST or ALT and total bilirubin, and the composite endpoint of AST or ALT, total bilirubin, and ALP, subjects will be counted once when the criteria are met at the same postbaseline visit date. The denominator is the number of subjects in the Safety Analysis Set with nonmissing postbaseline

value of the tests in evaluation at the same postbaseline visit date. Subjects with AST or  $ALT > 3 \times ULN$ , total bilirubin  $> 1 \times ULN$ , or  $ALP > 1.5 \times ULN$  while on-treatment) as well as subjects with treatment-emergent Grade 3 or 4 ALT, AST, ALP, and total bilirubin ) will also be listed.

In addition, baseline, postbaseline, and change from baseline in AST, ALT, ALP, and total bilirubin will be summarized by treatment group and visit using descriptive statistics.

### 7.3. Bone Mineral Density

BMD data will be summarized for the subjects in the hip or spine DXA analysis sets including on-treatment data collected up to 30 days after permanent discontinuation of study drug and all available data for subjects who were still on study drug or on a study drug interruption.

### 7.3.1. Percentage Change from Baseline in Hip and Spine Bone Mineral Density

Percentage change from baseline in hip and spine BMD at Week 48 using observed on-treatment data are 2 of the 6 key (α-controlled) secondary endpoints.

The percentage change from baseline in hip BMD and spine BMD will be summarized for on-treatment data (ie, data collected up to 30 days after permanent discontinuation of study drug or all available data for subjects who were still on study drug) using observed data by treatment group and visit using descriptive statistics for subjects in the Hip and Spine DXA Analysis Sets, respectively, and compared between the 2 treatment groups at each visit using ANOVA, which includes baseline F/TDF for PrEP and treatment as fixed effects.

As a sensitivity analysis, hip BMD and spine BMD based on on-treatment data using the LOCF and BIOCF methods will be summarized using the Hip and Spine DXA Analysis Sets.

Median (Q1, Q3) and mean (95% CI) of the percentage change from baseline in hip BMD and spine BMD over time using observed data will be plotted by treatment group. Listings of hip and spine DXA results will be provided.

## 7.3.1.1. Subgroup Analysis for Percentage Change from Baseline in Hip and Spine Bone Mineral Density

The percentage change from baseline in hip and spine BMD will be summarized for on-treatment data using observed data by treatment group and visit within each subgroup specified in Section 3.4.2 [by baseline F/TDF for PrEP medications]. Baseline and percentage change from baseline will be compared by visit between the 2 treatment groups using ANOVA, which includes baseline F/TDF for PrEP and treatment as fixed effects for the age subgroups or only treatment as a fixed effect for the baseline F/TDF for PrEP subgroups.

### 7.3.2. Hip and Spine BMD Clinical Status

Analysis of hip and spine BMD clinical status will be based on the observed BMD values (ie, missing will be excluded).

For each subject and each visit, the BMD clinical status will be defined for hip BMD and spine BMD as follows based on the t-score from a male reference population:

Table 7-1. Normal, Osteopenia, and Osteoporosis as Defined by T-score

Clinical Status	BMD T-score
Normal	$T$ -score $\geq -1.0$
Osteopenia	-2.5 ≤ T-score < -1.0
Osteoporosis	T-score < -2.5

The number and percentage of subjects in each BMD clinical status (normal, osteopenia, and osteoporosis) will be summarized by visit and by baseline clinical status for both hip and spine. The distribution of the BMD clinical status will be compared between the 2 treatment groups adjusting for baseline clinical status and baseline F/TDF for PrEP using rank analysis of covariance {LaVange 2008}.

### 7.3.3. Gradation of the Percentage Change in Hip, Femur Neck, and Spine BMD

For each subject and each visit, percentage change from baseline in spine BMD will be classified into 6 categories:  $\geq 5\%$  decrease,  $\geq 3\%$  to < 5% decrease, > 0% to < 3% decrease,  $\geq 0\%$  to < 3% increase,  $\geq 3\%$  to < 5% increase, and  $\geq 5\%$  increase. Similarly, the percentage change from baseline in hip BMD and femur neck BMD will be classified into 6 categories:  $\geq 7\%$  decrease,  $\geq 3\%$  to < 7% decrease, > 0% to < 3% decrease,  $\geq 0\%$  to < 3% increase,  $\geq 3\%$  to < 7% increase, and  $\geq 7\%$  increase. The number and percentage of subjects in each category will be summarized by visit. The difference in the distribution of these categories between the treatment groups will be compared using a CMH test (row mean scores differ statistic) adjusting for baseline F/TDF for PrEP.

In addition, the number and percentage of subjects with percentage change from baseline in each cumulative categories (ie,  $\geq$  5% decrease,  $\geq$  3% decrease, no decrease [ $\geq$  0% increase],  $\geq$  3% increase, and  $\geq$  5% increase for spine BMD;  $\geq$  7% decrease,  $\geq$  3% decrease, no decrease [ $\geq$  0% increase],  $\geq$  3% increase, and  $\geq$  7% increase for hip and femur neck BMD) will be compared between treatment groups using a CMH test (general association statistic) adjusting for baseline F/TDF for PrEP based on the dichotomized response (ie,  $\geq$  5% decrease vs. < 5% decrease).

### 7.4. Renal-Related Safety Evaluations

Renal-related laboratory data will be summarized for the subjects in the Safety Analysis Set including on-treatment data collected up to 30 days after permanent discontinuation of study drug and all available data for subjects who were still on study drug or on a study drug interruption.

## 7.4.1. Beta-2-Microglobulin to Creatinine Ratio, Urine Retinol Binding Protein to Creatinine Ratio, Urine Creatinine

Percentage change from baseline in renal biomarkers of beta 2-microglobulin to creatinine ratio and urine RBP to creatinine ratio at Week 48 using observed on-treatment data are 2 of the 6 key ( $\alpha$ -controlled) secondary endpoints.

Baseline, postbaseline, change from baseline, and percentage change from baseline in beta-2 microglobulin to creatinine ratio and urine RBP to creatinine ratio will be summarized for on-treatment data (ie, data collected up to 30 days after permanent discontinuation of study drug or all available data for subjects who were still on study drug) using observed data by treatment group and visit using descriptive statistics. Baseline and percentage change from baseline will be compared between the 2 treatment groups using a Van Elteren test stratified by baseline F/TDF for PrEP at each visit.

Baseline, postbaseline, and change from baseline in urine creatinine will be summarized by treatment group and visit using descriptive statistics. Baseline and change from baseline will be compared between the 2 treatment groups using a Van Elteren test stratified by baseline F/TDF for PrEP at each visit.

As a sensitivity analysis, renal biomarkers of beta 2-microglobulin to creatinine ratio and urine RBP to creatinine ratio based on on-treatment data using the LOCF and BlOCF methods will be summarized.

Median (Q1, Q3) percentage change from baseline in beta-2 microglobulin to creatinine ratio and urine RBP to creatinine ratio over time using observed data will be plotted by treatment group.

# 7.4.1.1. Subgroup Analysis for Beta-2-Microglobulin to Creatinine Ratio and Urine Retinol Binding Protein to Creatinine Ratio

The analysis of baseline, postbaseline, change from baseline, and percentage change from baseline in beta-2 microglobulin to creatinine ratio and urine RBP to creatinine ratio will be summarized by treatment group and visit within each baseline F/TDF for PrEP medications subgroup specified in Section 3.4.2. Baseline and percentage change from baseline will be compared between the 2 treatment groups using a 2-sided Wilcoxon rank sum test at each visit.

### 7.4.2. Proteinuria by Quantitative Assessment

The distribution of the UP and UPCR categories at Week 48 using observed on-treatment data is 1 of the 6 key ( $\alpha$ -controlled) secondary endpoints.

Subjects will be classified into three categories based on their urine protein (UP) and urine protein to creatinine ratio (UPCR) results: UPCR  $\leq$  200 mg/g (including subjects with UP < 4.0 mg/dL), UPCR > 200 mg/g, and Missing, where UPCR will only be calculated when UP  $\geq$  4.0 mg/dL. The number and percentage of subjects in each UP and UPCR category will be summarized for on-treatment data at Weeks 48 and 96 using observed data by baseline category

{KDIGO Guideline Development Staff 2013}. The distribution of the UP and UPCR categories will be compared by visit between the 2 treatment groups adjusting for baseline categories and baseline F/TDF for PrEP using rank analysis of covariance{LaVange 2008} (Appendix 2).

As a sensitivity analysis, UP and UPCR categories by visit based on on-treatment data using the LOCF and BlOCF methods will be summarized.

### 7.4.2.1. Subgroup Analysis for Proteinuria by Quantitative Assessment

The distribution of the UP and UPCR categories will be summarized for on-treatment data using observed data by treatment group at Week 48 and 96 within each baseline F/TDF for PrEP medications subgroup specified in Section 3.4.2. The distribution of the UP and UPCR categories will be compared by visit between the 2 treatment groups adjusting for baseline categories using rank analysis of covariance.

### 7.4.3. Proteinuria by Urinalysis (Dipstick)

The distribution of treatment-emergent proteinuria toxicity grade at the highest postbaseline graded value will be compared between treatment groups adjusting for baseline proteinuria toxicity grade and baseline F/TDF for PrEP using rank analysis of covariance {LaVange 2008}.

### 7.4.3.1. Subgroup Analysis for Proteinuria by Urinalysis (Dipstick)

The distribution of treatment-emergent proteinuria toxicity grade at the highest postbaseline graded value will be compared between treatment groups within each subgroup specified in Section 3.4.2. Comparisons between treatment groups will be adjusted for baseline F/TDF for PrEP (except for subgroups by baseline F/TDF for PrEP) and baseline proteinuria toxicity grade using rank analysis of covariance {LaVange 2008} at each visit.

#### 7.4.4. Serum Creatinine

Change from baseline in serum creatinine at Week 48 using observed on-treatment is 1 of the 6 key ( $\alpha$ -controlled) secondary endpoints.

Baseline, postbaseline, and change from baseline in serum creatinine will be summarized for on-treatment data using observed data by treatment group and visit using descriptive statistics. Baseline serum creatinine will be compared between the 2 treatment groups using ANOVA, which includes baseline F/TDF for PrEP and treatment as fixed effects. Change from baseline will be compared between the 2 treatment groups using an analysis of covariance model (ANCOVA) that includes baseline F/TDF for PrEP and treatment as fixed effects and baseline serum creatinine as a covariate.

As a sensitivity analysis, serum creatinine based on on-treatment data using the LOCF and BIOCF methods will be summarized.

Median (Q1, Q3) and mean (95% CI) of change from baseline in serum creatinine over time using observed data will be plotted by treatment group.

### 7.4.5. eGFRcg

Baseline, postbaseline, and change from baseline in eGFRCG will be summarized by treatment group and visit using descriptive statistics. Baseline and change from baseline will be compared between the 2 treatment groups using a Van Elteren test stratified by baseline F/TDF for PrEP at each visit.

Median (Q1, Q3) of change from baseline in eGFRCG over time will be plotted by treatment group.

### 7.4.5.1. Subgroup Analysis for eGFRCG

The analysis of baseline, postbaseline, and change from baseline in eGFRCG will be summarized by treatment group and visit using descriptive statistics within each subgroup specified in Section 3.4.2. Baseline and change from baseline will be compared between the 2 treatment groups using a 2-sided Wilcoxon rank sum test for the subgroup of baseline F/TDF for PrEP and a Van Elteren test stratified by baseline F/TDF for PrEP for all other subgroups at each visit.

### 7.4.6. Proximal Renal Tubulopathy

Treatment-emergent proximal renal tubulopathy (PRT) events will be summarized by treatment group using the Safety Analysis Set by the following PTs (Appendix 10):

- Fanconi syndrome
- Fanconi syndrome acquired
- Renal tubular disorder
- Renal tubular dysfunction
- Renal tubular injury

The number and percentage of subjects who experienced PRT events will be summarized by treatment group and PT and compared between the 2 treatment groups using Fisher's exact test.

### 7.5. Body Weight, Height, BMI and Vital Signs

Descriptive statistics will be provided by treatment group for body weight, BMI and vital signs as follows:

- Baseline values
- Values at each postbaseline analysis window
- Change from baseline to each postbaseline analysis window

A baseline value will be defined as the last nonmissing value obtained on or prior to the date of first dose of study drug. Change from baseline to a postbaseline visit will be defined as the postbaseline value minus the baseline value.

In the case of multiple values in an analysis window, data will be selected for analysis as described in Section 3.8.3.

For body weight and BMI, baseline values will be compared between the 2 treatment groups using ANOVA, which includes baseline F/TDF for PrEP and treatment as fixed effects while change from baseline and percentage change from baseline (for body weight only) will be compared by visit between the 2 treatment groups using ANCOVA, which includes baseline F/TDF for PrEP and treatment as fixed effects and baseline value as a covariate.

For vital signs, no formal statistical testing is planned.

A by-subject listing of vital signs will be provided by subject ID number and visit in chronological order. In the same listing, a by-subject listing of body weight, height, and BMI will be provided.

#### 7.6. Prior and Concomitant Medications

### 7.6.1. Nonstudy Drug Antiretroviral Medications

Any nonstudy drug antiretroviral (ARV) medications used prior to, during, or after the study (if collected) will be coded using the current version of the Gilead-modified World Health Organization (WHO) Drug Dictionary for ARV medications. The WHO preferred name and drug code will be attached to the clinical database. All nonstudy drug ARV medications will be listed. No inferential statistics will be provided.

#### 7.6.2. Prior F/TDF for PrEP Medications

Prior F/TDF for PrEP medications are defined as any treatment course that includes branded F/TDF or generic F/TDF without any other 3rd ARV agents received prior to or on the first dose date of study drug.

The number and percentage of subjects with any prior F/TDF for PrEP (branded or generic F/TDF) will be summarized by treatment group and overall with other baseline HIV risk characteristics in Section 5.3.

For prior F/TDF for PrEP, medications with a start date prior to the first dosing date of study drug will be included regardless of the stop date. If a partial start date is entered, the medication will be considered prior unless the month and year (if day is missing) or year (if day and month are missing) of the start date are after the first dosing date. Medications with a completely missing start date will be included in the prior medication summary.

### 7.6.3. Baseline F/TDF for PrEP Medications

Baseline F/TDF for PrEP medications (ie, recent relative to Study Day 1) are defined as any treatment course that includes branded F/TDF or generic F/TDF without any other 3rd ARV agents with an end date between Screening and first dose date (inclusive) of study drug.

The number and percentage of subjects with baseline F/TDF for PrEP (branded or generic F/TDF) will be summarized by treatment group and overall with other baseline HIV risk characteristics in Section 5.3.

For baseline F/TDF for PrEP, medications with a partial end date entered will be considered as a baseline medication if the month and year (if day is missing) of the end date is either between or the same as either the screening date or first dose date. Medications with a completely missing or year only end date will not be considered as a baseline medication.

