#### 3.3. Strata and Covariates

This study does not use a stratified randomization schedule when enrolling subjects. Analyses of BMD, renal safety endpoints, weight and BMI will be adjusted for baseline F/TDF for PrEP.

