### 7.6.4. PEP Medications While At Risk of HIV Infection During the Study

Post-exposure prophylaxis (PEP) is defined as treatment with any non-study drug ARV agent other than F/TDF (or generic F/TDF), cabotegravir or HIV vaccine while subjects are at risk of HIV infection as defined in Section 6.2.3.

The number of subjects with any PEP use and the number of PEP uses per subject while at risk of HIV infection during the DB phase, while on-treatment and while off-treatment and at risk of HIV infection will be summarized for the FAS.

The number of PEP uses per subject will be based on unique PEP medication start dates within each subject. Multiple ARV medications with overlapping start and end dates will be counted as only one PEP use. Consecutive PEP medications where the complete medication end date of one PEP medication differs from the complete medication start date of another PEP medication by one day or less will be counted as only one PEP use.

For PEP uses while at risk of HIV infection during the DB phase, if the start or stop date of the ARV medication is incomplete, the month and year (or year alone, if month is not recorded) of the start or stop date will be used to determine whether the ARVs occurred during the at risk of HIV infection period or not. The medication occurred during the at risk of HIV infection period if the month and year of the start or stop (or year of the start or stop, if month is not recorded) of the medication does not meet either of the following criteria:

- The month and year of start of the medication is after the date of the end of the at risk of HIV infection period
- The month and year of stop of the medication is on or before the date of the first dose of study drug

If the start and stop date of ARV medications are complete, the start date is not after the date of the end of the at risk of HIV infection period and the stop date is not on or before first dose date, or the ARV medications are marked as ongoing and start date is on or before the date of the end of the at risk of HIV infection period, the non-ARV medications are considered as occurring during the at risk of HIV infection period. Medications with completely missing start and end dates will not be considered as occurring while at risk of HIV infection during the study.

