## 30) Lipid modifying medication analyses:

- a) Lipid modifying medication is defined to be the concomitant medication with ATC2 CMCLAS term "LIPID MODIFYING AGENTS" and CMDECOD contains wording of "STATIN" in the ADCM dataset.
- b) Subjects who took lipid-modifying medications at study entry refer to the subjects who use of the lipid-modifying agents at study day 1 (ie, the first dose date). More specifically, subjects with "Lipid Modifying Agent Use at Study Entry" include those subjects in Safety Analysis Set with: 1) any selected CM record with the start date ≤ the first dose date, and 2) the end date of the selected CM record is ongoing or the end date of the selected CM record > the first dose date.
- c) Subjects who initiated lipid-modifying medications during the study include the subjects in the Safety Analysis Set who didn't take lipid-modifying medications at study entry and met the following criteria: 1) for subjects who permanently discontinued study drug with any selected CM record started after the first dose date and on and prior to the last dose date; 2) for subjects who are still on study drug with any selected CM records started after the first dose date.
- d) For lipid-modifying medications with the start date completely unknown, we assume the start date is on or before the first dose date, lipid-modifying medication was considered as being taken at study entry if the end date is not prior to the first dose date (ie, the end date is on or after the first dose date, completely unknown, or ongoing).
- e) Lipid modifying medications with the start date prior to the first dose date and the end date completely unknown were considered as being taken at study entry.
- 31) For figures, if at a visit where n (sample size) for any treatment group ≤ 5, data for that treatment group will not be displayed at the visit in figure (except the Kaplan-Meier figure), but all data will be included in the corresponding table summary.

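### The baseline F/TDF rule in SAP 7.6.3 looks only for an end date by first dose, so participants still on F/TDF at Day 1 are coded as non-users

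*SAP*

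**What the plan says.** SAP 7.6.3 introduces the variable as "Baseline F/TDF for PrEP medications (ie, recent relative to Study Day 1" and then defines it as a branded or generic F/TDF course, without a third antiretroviral, "with an end date between Screening and first dose date (inclusive) of study drug". An end date with month and year only counts if that month "is either between or the same as either the screening date or first dose date". The section closes with "Medications with a completely missing or year only end date will not be considered as a baseline medication". It sets no start-date condition and has no clause for courses marked as ongoing. Appendix 12 does not override it.

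The variable is used widely. SAP 3.3 states: "Analyses of BMD, renal safety endpoints, weight and BMI will be adjusted for baseline F/TDF for PrEP". It is a fixed effect for BMD (7.3.1), serum creatinine (7.4.4) and weight and BMI (7.5), the stratum in the Van Elteren tests for renal biomarkers and eGFR (7.4.1, 7.4.5), and an adjustment factor for the UPCR categories (7.4.2). It also defines the Yes/No subgroups for HIV incidence (3.4.1) and for bone, renal and metabolic safety (3.4.2).

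Neighbouring rules are written differently:

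- For any prior F/TDF, 7.6.2 says "medications with a start date prior to the first dosing date of study drug will be included regardless of the stop date".
- For PEP, 7.6.4 names the ongoing case: "the ARV medications are marked as ongoing and start date is on or before the date of the end of the at risk".
- For lipid drugs, Appendix 12 item 30(b) counts use at study entry if the course started by first dose and is ongoing or ended later. Item 30(e) does the same for records with an earlier start and "the end date completely unknown were considered as being taken at study entry".

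**The concern.** The variable is meant to identify recent F/TDF exposure, yet the rule gives the non-user code to the most recent exposure of all. Someone who stopped on the day of Screening is Yes, and someone still taking F/TDF after the first study dose is No. For courses running at Day 1, a baseline factor is decided by a stop date after baseline.

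What is at stake is what the two groups mean. In the No group, F/TAF versus F/TDF should be a contrast between starting one drug and starting the other. In the Yes group it is closer to switching away from TDF versus staying on it. The Protocol's Study Procedures Table (Appendix 2) schedules chemistry and urine tests at Screening but not on Day 1, and SAP 3.8.1 takes the last value on or before Day 1 as baseline. A participant on F/TDF throughout screening therefore brings TDF-affected baselines into the No group. The subgroup analyses cannot adjust for this: within these subgroups they use treatment alone (7.3.1.1) or an unstratified Wilcoxon test (7.4.1.1).

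**Working it through.** **1. The rule applied to examples.** Take Screening on 10 January 2017, first dose on 30 January 2017, and a course begun before Screening (dates chosen for illustration).

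| Recorded end of F/TDF course | Coding under 7.6.3 | On F/TDF at Day 1? |
|---|---|---|
| 9 January | No | No |
| 29 January | Yes | No, stopped the day before |
| 30 January | Yes | Until that day |
| 31 January | **No** | **Yes** |
| February 2017 (month and year) | **No** | **Yes** |
| Ongoing | **No** (no end date to qualify) | **Yes** |
| January 2017 (month and year) | Yes | Possibly |
| 2017 (year only) | No, by explicit clause | Unknown |
| Completely missing | No, by explicit clause | Unknown |

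The rows in bold contradict the section's stated meaning. There is also an inconsistency of precision: a course that ended on 31 January is No if the full date is recorded and Yes if only January 2017 is recorded.

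**2. Can such records occur?** In the readable text of Protocol 4.2, 4.3 and Table 5-1, I found no requirement that F/TDF for PrEP has stopped by Day 1. SAP 6.2.6 anticipates non-study PrEP with ongoing stop dates, although mainly for use after study drug ends. The records are possible; their number is not given.

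**3. Possible size (assumed inputs).** Let p be the share of participants on F/TDF around entry and m the share of those coded No. The share of the No group who are users is p·m / (1 − p + p·m).

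| p | m = 2% | m = 10% | m = 25% |
|---|---|---|---|
| 5% | 0.11% | 0.52% | 1.30% |
| 15% | 0.35% | 1.73% | 4.23% |
| 30% | 0.85% | 4.11% | 9.68% |

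The middle case is 0.15 × 0.10 / (0.85 + 0.015) = 1.73%. With the 5387 participants in the Safety Analysis Set (SAP Appendix 3), that is 0.015 × 5387 ≈ 81 people. The corners are 0.001 × 5387 ≈ 5 and 0.075 × 5387 ≈ 404. Neither p nor m comes from the documents.

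**4. Effect on the overall adjusted comparison.** No stated figure depends on this rule. As a check on the setting, the DXA power in SAP 1.3.1 was recomputed: 200 per arm, difference 1.54%, SDs 3.05% and 3.15% (pooled √((3.05² + 3.15²)/2) = 3.10), two-sided 0.01. The standard error is 3.10 × √(2/200) = 0.31, and 1.54/0.31 − 2.576 = 2.39, so power is 99.2%, consistent with the stated minimum of 95%.

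The adjusted ANOVA was then simulated with 200 per arm, p = 15% and users' BMD change shifted by 1.5 percentage points (both assumed). There were 20,000 runs for type I error and 5,000 for power.

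| Users miscoded | Type I error (nominal 0.01) | Power at a 1.0% difference |
|---|---|---|
| 0% | 0.0100 | 74.0% |
| 25% | 0.0097 | 74.1% |
| 50% | 0.0097 | 73.0% |

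The simulation error of each power figure is about √(0.74 × 0.26/5000) = 0.6 points, so the movement is close to noise. The simulation assumes the same treatment effect in users and non-users. It therefore speaks to the overall test and not to the subgroups.

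**The case against.** The strongest case against has five parts.

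- **Rarity.** Study drug replaces F/TDF, so most courses should end by Day 1 and the gap may touch few people. This stands as a limit on size.
- **Secondary use.** The safety subgroups are optional under SAP 3.4.2, and the HIV subgroup analysis (6.2.7) gives within-arm rates with no between-arm test. This also stands and keeps the point modest.
- **Ongoing is not named.** SAP 7.6.3 does not mention ongoing courses, and Appendix 12 elsewhere separates ongoing from unknown end dates. For those records the text is better called a missing clause whose literal result is No. For full end dates after first dose, No follows directly.
- **Different purpose.** Lipid drugs may run alongside study drug, so their rule need not carry over. That is fair for undated records. It does not explain why a course known to run past first dose fails to count as recent.
- **Timing.** SAP section 1 says that the primary analysis is already reported and unblinded. Silently replacing the covariate would break continuity, so both codings should be shown.

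A reader might also infer that coding missing or year-only end dates as No is an error of the same kind. The documents do not support that. Some of those people may have stopped long before Screening. Enrolment ran from September 2016 to June 2017 (SAP Appendix 9), so an end date recorded only as 2016 could precede a December 2016 entry by most of a year. SAP 7.6.4 likewise drops antiretroviral records with neither start nor end date. Errors also weigh more in the smaller group. If 10% of 5387 are users, 50 past users wrongly coded Yes are 50/(539 + 50) = 8.5% of that group, while 50 current users wrongly coded No are 50/(4848 + 50) = 1.0% of theirs.

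**Conclusion.** The point holds for courses begun on or before first dose that ended after it, and on a literal reading for courses recorded as ongoing. The rule codes both No, against its own stated meaning. The 0.1-9.7% range for contamination of the No group rests wholly on assumed values, and the true figure may be at or below the low end.

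It would be tempting to conclude that the treatment comparisons are biased. They are not: the same rule applies in both arms under blinding, randomisation was not stratified on this variable (SAP 3.3), and the simulated adjusted test kept its error rate with almost unchanged power. The harm is confined to what the Yes and No subgroups represent and to slightly weaker adjustment. The change is worth making because it is cheap and because the subgroups are the plan's means of separating people starting PrEP from people already on TDF.

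**What to change.** In SAP 7.6.3, define baseline F/TDF for PrEP as any F/TDF course without a third antiretroviral that started on or before the first dose date and is either ongoing or has an end date on or after Screening. The start-date condition keeps out courses begun later. Compare month-and-year end dates by month, as now, but without the upper limit at first dose.

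Keep the No coding for completely missing and year-only end dates in the main definition, state that an ongoing record is not a missing one, and code the undated records Yes in a sensitivity analysis.

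Because the primary analysis is already reported, also show the affected results under the current definition and report by arm how many participants change category. If few move, that count settles the matter.

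The cost is one revised sentence, one extra derivation, the sensitivity run, and a small departure from the coding now in this SAP.
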